# **Primary Outcome**

The primary outcome, PrEP adherence obtained through DBS, is a binary variable and will be analyzed using a GLMM with a logit link function. The intervention effect will be represented by an adjusted odds ratio, and will be assessed across different follow-up points. This analysis will be implemented in R using the "glmer()" function, specifying a logit link and a random intercept for participants to account for within-subject correlations.

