# 3.3 Sample Size

The Prepare Romania trial's sample size was chosen to provide preliminary data on the hypothesized intervention outcomes, PrEP adherence and persistence among GBMSM in Romania, as well as to inform the design of a future effectiveness trial. A formal power calculation was not conducted due to the exploratory nature of this pilot study. Instead, we followed guidance from Whitehead et al., which provides recommendations for sample sizes in pilot studies.

The sample size of 60 participants per arm (120 total) was selected based on conservative effect size estimates drawn from previous studies evaluating PrEP adherence interventions. In a comparable RCT testing the SPARK intervention, protective PrEP levels (defined as adherence of ≥4 doses per week) were observed in 94% of the intervention arm and 85% of the control arm at the 3-month follow-up, with corresponding rates of 92% and 86% at 6 months. This difference in adherence rates translates to an estimated effect size of 6%, with a pooled standard deviation of approximately 0.32, yielding a standardized effect size of 0.19. Whitehead et al. suggest a minimum sample size of 25 participants per condition for pilot trials when the effect size falls between 0.1 and 0.3. To ensure adequate power, the Prepare Romania trial conservatively enrolls 60 participants per arm, exceeding this minimum and allowing for a robust assessment of intervention impact.

Each site (Bucharest and Cluj-Napoca) is tasked with recruiting 60 participants. With this sample size, the study expects retention at 6 months to exceed 25 participants per arm, even accounting for potential attrition. This estimate is supported by high retention rates (approximately 89%) reported in prior SPARK trials.

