# 6. Analysis

#### **6.1 Outcome Definitions**

# **Primary Outcome**

The primary outcome of this study is PrEP adherence, which will be measured objectively using dried blood spot (DBS) testing to detect levels of tenofovir diphosphate (TFVdp). Adherence is defined as achieving a TFVdp concentration of ≥1000 fmol/punch, corresponding to a mean dosing frequency of at least four doses per week. This measure will be evaluated at 3- and 6-months post-randomization. The binary operationalization of this measure will serve as the primary outcome.

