#### 6.2 Analysis Methods

We will use Generalized Linear Mixed Models (GLMMs) to handle the various types of outcomes across primary and secondary measures, which allows for fixed effects (intervention, site, time, baseline outcome, the interaction between intervention and time baseline covariates) and random effects (including participant-level variability). The adjusted covariates include age, relationship status, and PrEP usage. All analyses will be conducted in R. The general form of the GLMM is:

$$g(\mu(Y_{ij})) = \beta_1 I(Time_{ij} = 3) + \beta_2 I(Time_{ij} = 3) \times Intervention + \beta_3 I(Time_{ij} = 6) + \beta_4 I(Time_{ij} = 6) \times Intervention + \beta_5 Covariates_i + \mu_i + \epsilon_{ij}$$

 $Y_{ij}$  represents the outcome for participant i at time j,  $\mu(Y_{ij})$  is the expected value of  $Y_{ij}$  given the covariates,

g(.) is the link function that relates the linear predictors to the expected value of outcome (e.g., logit link for binary outcomes, identity link for continuous outcomes),

 $\beta_1$  is the effect of time at 3 month,

 $\beta_2$  is the interaction effect between intervention and time at 3 month,

 $\beta_3$  is the effect of time at 6 month,

 $\beta_4$  is the interaction effect between intervention and time at 6 month,

 $\beta_5$  is the covariate effect,

 $\mu_i$  is the random intercept for each participant, where  $\mu_i \sim N(0, \sigma_i^2)$ ,

I(.) is the indicator function.

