### Treatment effects from the model

3 month	6 month
$eta_2$	$eta_4$

Then the average treatment effect is

$$\frac{\beta_2 + \beta_2}{2}$$

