### **Secondary Outcomes**

The secondary outcomes include continuous, binary, and categorical variables, each analyzed with an appropriate link function based on the outcome type. For continuous outcomes, such as depression and anxiety symptomology scores, an identity link function will be used, estimating the intervention effect as the difference in mean scores between groups. This model will be implemented using the "lmer()" function in R. Binary secondary outcomes, will use the same logit link function and implementation details as the primary outcome analysis.

**Table 1.** List of secondary outcomes.

Variable coding
Continuous
Binary and continuous
Continuous
Continuous
Binary
Ordinal categorical, with 7 categories

PrEP stigma	Continuous
Positive attitudes/beliefs	Continuous
about PrEP	
Negative attitudes/beliefs	Continuous
about PrEP	
PrEP barriers	Continuous
PrEP facilitators	Continuous
STI diagnoses	Binary
CAS acts	Continuous

Each model will output the intervention effect at baseline, 3 months, and 6 months (with the exception of STI diagnoses and CAS acts, which are only measured at baseline and 6 months as well as DBS and self-report PrEP adherence, which are only measured at 3 months and 6 months), with 95% confidence intervals to provide estimates of precision.

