# **6.3 Missing Data**

Missing data are expected at follow-up time points (3 months and 6 months) in primary and secondary outcomes. Assuming that the missing data follow a Missing at Random (MAR) pattern, Multiple Imputation by Chained Equations (MICE) (Van Buuren and Groothuis-Oudshoorn 2011) will be used to handle missing values for the primary outcome and secondary outcome adjusting all baseline covariates. Imputations will be generated with 15 datasets using the "mice()" function from the "mice" package in R. The imputation methods will include predictive mean matching (pmm) for continuous outcomes, logistic regression (logreg) for binary outcomes, and polytomous regression (polyreg) for categorical outcomes. Each imputed dataset will be analyzed separately, and results will be combined using Rubin's Rules(Rubin 2004) to obtain pooled estimates and confidence intervals, accounting for the variability within and between imputations.

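### SAP 6.2 names glmer() but no integration order; with two binary results per man, the default Laplace fit can cost precision in the primary analysis if adherence is as high as planned and men differ widely

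*SAP*

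**What the plan says.** SAP 6.2 (Primary Outcome) fits DBS adherence as a binary variable with glmer(), "specifying a logit link and a random intercept for participants to account for within-subject correlations". It gives no number of quadrature points, no optimizer and no rule for fits that warn. Binary secondary outcomes "will use the same logit link function and implementation details as the primary outcome analysis".

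Each man contributes little to this model. SAP 6.1 says of the primary outcome: "This measure will be evaluated at 3- and 6-months post-randomization". SAP 6.2 (Secondary Outcomes) confirms that there is no baseline value: "DBS and self-report PrEP adherence, which are only measured at 3 months and 6 months".

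The model has separate intervention effects at 3 months (beta2) and 6 months (beta4). On adjustment, SAP 6.2 states: "The adjusted covariates include age, relationship status, and PrEP usage"; site is also a fixed effect. After the words "Then the average treatment effect is", the formula prints beta2 twice; I read it as (beta2 + beta4)/2. SAP 6.3 adds multiple imputation: "Imputations will be generated with 15 datasets".

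The only adherence rates are those in SAP 3.3 from an earlier trial of the counselling component. Protective levels "were observed in 94% of the intervention arm and 85% of the control arm at the 3-month follow-up", and in 92% and 86% at 6 months. Neither document gives a random-intercept SD or a within-man correlation.

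**The concern.** The Laplace method replaces each man's integral over the random intercept by a one-point approximation. It is weakest when each cluster holds few binary records and most of them are equal, and two records per man with planned adherence of 85% to 94% is that situation. The fitted SD can then move to a false large value and widen the standard error of the conditional log odds ratio.

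The primary analysis is affected. At stake are the width of the interval, power, and the value of the estimate for planning the later effectiveness trial. A second issue is that two analysts who both follow the SAP could choose different integration orders and reach different decisions at 0.05.

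**Working it through.** **The plan's own figure.** SAP 3.3 gives 0.06/0.32 = 0.1875, which rounds to the stated 0.19. The documents give no power or standard error for the average effect, so there is no further figure to reproduce.

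**Inputs.** From SAP 3.3: 60 per arm; control 85% and 86%, intervention 94% and 92%, at 3 and 6 months. Expected non-adherent men:
- 3 months: 60 × 0.15 + 60 × 0.06 = 9 + 3.6 = 12.6
- 6 months: 60 × 0.14 + 60 × 0.08 = 8.4 + 4.8 = 13.2

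Assumed: the between-man SD. As a guide, SD 1.5 is a latent correlation of 1.5²/(1.5² + 3.29) = 0.41. A control man non-adherent at 3 months then has a 32% chance of being non-adherent at 6 months. That chance is 23% at SD 1 and 14% if visits were independent.

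**Method.** The model is logit P(Y = 1) = visit intercept + visit-specific arm effect + u, with u ~ N(0, SD²). The conditional coefficients are solved so that the marginal rates equal those above. The model is then fitted to the expected cell counts by Laplace and by adaptive Gauss-Hermite quadrature (15 to 61 points; 61 for SD 3 and 4). The standard error of (beta2 + beta4)/2 comes from the joint Hessian of the coefficients and the SD.

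**Expected data at the planning rates, no covariates.**

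| Assumed SD | Laplace SE | Quadrature SE | Ratio | SD fitted by Laplace |
|---|---|---|---|---|
| 0.5 | – | – | 1.10 | 1.02 |
| 1 | 0.587 | 0.520 | 1.13 | 1.53 |
| 1.2 | 0.986 | 0.552 | 1.79 | 4.88 |
| 1.5 | 1.100 | 0.609 | 1.81 | 5.98 |
| 2 | 1.255 | 0.723 | 1.74 | 7.39 |
| 3 | 1.536 | 0.999 | 1.54 | 9.82 |
| 4 | 1.787 | 1.313 | 1.36 | 11.98 |

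The estimate does not grow with the standard error. At SD 1.5 the average log odds ratio is 1.00 (Laplace) and 1.01 (quadrature), so z = 1.00/1.100 = 0.91 against 1.01/0.609 = 1.66.

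**Lower adherence (assumed rates, same at both visits).**
- 78% v 88%: ratio 1.02 at SD 1.5 and 1.60 at SD 2.
- 70% v 85%: ratio 0.96 at SD 1.5, 1.04 at SD 2 and 1.55 at SD 2.5.
- 60% v 80%: 0.92 to 1.04 for SD 1 to 2.5.

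**Single data sets.** The ratio is bimodal, near 1.0 to 1.2 or near 1.8 to 2.0. In lme4 at SD 1.5 without covariates (60 per arm, 79 trials) the median was 1.75, and 62% of trials reached 1.5. With four null covariates and 53 per arm (about 89% retention; 58 trials) the median was 1.22, interquartile range 1.03 to 1.88.

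**Runs closest to the plan.** These used lme4 1.1.37, site and the SAP covariates (with null effects), bobyqa for both methods, 15 imputations and Rubin's rules. Assumed missingness was 11% at 6 months (from 89% retention) and 6.6% at 3 months, completely at random. The imputation was coded by hand after the logistic method of mice.
- SD 1.5, 53 trials: significant average effect in 7 (Laplace) against 12 (quadrature); 5 decisions differ (5/53 = 9%); median pooled SE 1.00 against 0.66.
- SD 1, 39 trials: 13 against 16; 3 differ (8%); median pooled SE 0.65 against 0.58.

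**Covariate-free model with 15 imputations, labelled as such.** At SD 1.5 power was 30/188 = 16% against 66/188 = 35%, and 36/188 = 19% of decisions differed. Single-visit decisions differed in 16% (3 months) and 8% (6 months). Coverage for the average effect, over the SDs run, was 97% to 100% against 95% to 98%.

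**The case against.** **The SAP leaves the argument open.** An unstated setting does not commit the sponsor to the default, and a fitted SD of 6 or more would be visible to an alert analyst. This is fair. It is also the reason to fix the setting beforehand, so that it is not chosen after both fits have been seen.

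**The result needs both a large SD and the planning rates.** This stands. Men who stop PrEP would raise the agreement between visits and so the SD. The same men lower adherence, which raises the SD at which inflation starts. SAP 3.2 foresees men who forgo PrEP after randomization, and SAP 4.2 analyses by intention to treat, so adherence below 85% to 94% is plausible.

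**The evidence closest to the plan is thin.** This stands. Five differing decisions, all in one direction, give an exact McNemar p of 2 × 0.5⁵ = 0.06. Among trials with no Laplace warning, 4 of 36 (SD 1.5) and 2 of 34 (SD 1) still differed.

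**The average is not named as the primary test.** This also stands. SAP 6.2 assesses the effect at the separate follow-up points too, where decisions differed less often.

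A reader might infer that the planned analysis would reverse its decision in about a fifth of trials. The documents do not support this: the 19% comes from a model without the adjustment that SAP 6.2 requires. Nor does the 1.5 to 1.8 range hold for every larger SD; the ratio drops below 1.5 above about SD 3.2. Nor do these results show too many false positives. At the planning rates the error is conservative, and no type I error claim is made.

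**Conclusion.** The omission is real, and the default is a poor choice for two binary records per man. If adherence is near the planning rates and the between-man SD is about 1.5 to 3, the expected-data standard error of the average log odds ratio is about 1.5 to 1.8 times what quadrature gives. With covariates and 53 per arm, the typical single-trial ratio at SD 1.5 is nearer 1.2, with a wide spread. At SD 1 or below the expected-data loss is about 10% to 13%. At adherence of 70% to 88% it appears only from about SD 2 to 2.5.

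These sizes rest on an SD that the documents do not give, on rates from another trial, and on reading the average as (beta2 + beta4)/2. SAP 3.3 describes an exploratory pilot without a power calculation, and power stays low with the better fit (12 of 53 in the runs closest to the plan). The point is minor, but the change costs almost nothing.

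**What to change.** Add to SAP 6.2: 'Binary outcomes with two or more modelled records per participant will be fitted by glmer() with adaptive Gauss-Hermite quadrature (nAGQ = 15) and the bobyqa optimizer in every imputed data set, and the fit will be checked for stability at a higher quadrature order (for example 25). Singular fits are kept; a fit with a non-singular convergence warning is refitted from other starting values or with another optimizer before pooling.'

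Singular fits should be kept because a zero random-intercept variance reduces the model to ordinary logistic regression, and such fits are common. At least one of the 15 was singular in 15 of 53 trials (28%) at SD 1.5 and in 22 of 39 (56%) at SD 1. None of the 1,380 quadrature fits (92 trials × 15) gave a non-singular warning, so the refit step was not exercised.

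A marginal-model fallback and a rule for arm-by-visit cells with no non-adherent man are optional. The first was never needed in these runs. The second would replace the adjusted odds ratio that the SAP specifies.

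The cost is two function arguments, a short rule and a slightly longer run time. The change does not cure low power, and an empty cell still gives no finite odds ratio.

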### **Secondary Outcomes**

The secondary outcomes include continuous, binary, and categorical variables, each analyzed with an appropriate link function based on the outcome type. For continuous outcomes, such as depression and anxiety symptomology scores, an identity link function will be used, estimating the intervention effect as the difference in mean scores between groups. This model will be implemented using the "lmer()" function in R. Binary secondary outcomes, will use the same logit link function and implementation details as the primary outcome analysis.

**Table 1.** List of secondary outcomes.

Variable coding
Continuous
Binary and continuous
Continuous
Continuous
Binary
Ordinal categorical, with 7 categories

PrEP stigma	Continuous
Positive attitudes/beliefs	Continuous
about PrEP	
Negative attitudes/beliefs	Continuous
about PrEP	
PrEP barriers	Continuous
PrEP facilitators	Continuous
STI diagnoses	Binary
CAS acts	Continuous

Each model will output the intervention effect at baseline, 3 months, and 6 months (with the exception of STI diagnoses and CAS acts, which are only measured at baseline and 6 months as well as DBS and self-report PrEP adherence, which are only measured at 3 months and 6 months), with 95% confidence intervals to provide estimates of precision.

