# 3. Study Methods

### 3.1 Trial Design

The Prepare Romania trial is a two-arm, parallel-group randomized controlled trial (RCT) with a 1:1 allocation ratio, designed to evaluate the effectiveness of a culturally adapted intervention to improve adherence to PrEP among GBMSM in Romania. Participants are randomized to either the intervention or control arm. The intervention arm includes a combination of counseling and a culturally tailored mobile health app that supports PrEP adherence. Participants in the control arm receive standard PrEP education only. Randomization is stratified by city (Bucharest and Cluj-Napoca), and the study is unmasked, with both participants and staff aware of group assignments. Primary and secondary outcomes will be collected at baseline, 3 months, and 6 months post-randomization.

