# 4. Statistical Principles

#### 4.1 Confidence Intervals and P-Values

For the Prepare Romania trial, statistical analyses will be conducted with a two-sided significance level set at 0.05. This alpha level applies to all primary and secondary outcomes, ensuring that results are interpreted consistently across study endpoints. The 95% confidence intervals will be calculated for the primary and other key secondary outcomes.

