## **Secondary Outcomes**

The secondary outcomes include continuous DBS PrEP adherence, self-reported PrEP adherence (binary and continuous), PrEP knowledge (binary: all questions answered correctly vs. not), PrEP motivation (ordinal categorical), PrEP attitudes and beliefs (continuous), PrEP barriers, PrEP facilitators (continuous), PrEP stigma (continuous), anxiety symptomology (continuous), depression symptomology (continuous), STI diagnoses in the last 6 months (binary: any vs. none), and number of condomless anal sex (CAS) acts with HIV-positive or unknown-status partners in the last 6 months (continuous). For all secondary outcomes, missing data will be recorded and addressed.

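### SAP 6.2 is inconsistent on whether baseline is a covariate or a response; for CAS acts and STI diagnoses, with one follow-up each, neither resulting model is sound

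*SAP*

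**What the plan says.** SAP 6.2 (Analysis Methods) sets one mixed model for all outcomes. Its prose puts the baseline outcome among the fixed effects. Its equation has time indicators for months 3 and 6 only, each with an arm interaction, plus a residual and a further term that "is the random intercept for each participant".

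The secondary-outcomes part of SAP 6.2 assigns lmer() to continuous outcomes and carries the logit/glmer() implementation of the primary analysis over to binary ones. It says each model will report an arm effect at baseline, 3 months and 6 months. One exception covers "STI diagnoses and CAS acts, which are only measured at baseline and 6 months"; another covers the two adherence measures, which have no baseline value. The exceptions change which visits are reported. They do not change the model.

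SAP 6.1 treats the "number of condomless anal sex (CAS) acts with HIV-positive or unknown-status partners in the last 6 months (continuous") as continuous, so CAS falls to lmer(). STI diagnosis is binary and falls to glmer().

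SAP 4.1 fixes a "two-sided significance level set at 0.05" and adds: "This alpha level applies to all primary and secondary outcomes".

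**The concern.** The two parts of SAP 6.2 lead to different datasets. If baseline is a covariate, as the model description says, the only response left for CAS and STI is the 6-month value: one row per man. A participant intercept and a residual on one row are the same quantity for a linear model. The 3-month terms and the average of the 3- and 6-month effects are also undefined for these outcomes.

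If baseline is a response, as the promised baseline effect implies, there are two rows per man and the model can be fitted. The model description still asks for the baseline value as a covariate. An analyst who follows both instructions regresses baseline on itself in half of the rows. Those rows fit too well and pull the pooled residual variance down, so the standard error of the 6-month effect is too small.

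At stake are the two sexual-risk outcomes in the SAP. Neither has a coherent prespecified analysis, so the choice would be made at the time of analysis in an unmasked trial.

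**Working it through.** **Inputs from the SAP.** Two-sided alpha 0.05 (4.1); 120 men, 60 per arm, allocated 1:1 (3.1, 3.3); retention of about 89%, so 0.89 × 120 ≈ 107 men (3.3); CAS and STI at baseline and 6 months (6.2).

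**Assumptions.** The documents give no baseline to 6-month correlation (ρ) and no SDs for CAS. I take ρ from 0 to 0.9 with equal SDs, and a ratio k of 6-month to baseline SD from 0.5 to 2 at ρ = 0.5.

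**Nominal level.** 2 × (1 − Φ(1.96)) = 0.05, as stated in 4.1.

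**Reading 1: baseline as covariate only.** Run in R (lme4) with 120 single-row men, lmer() stops because the number of participants is not smaller than the number of observations. glmer() on a binary outcome with the same layout returns a fit. Imputing missing 6-month values does not add rows per man, so the imputation in SAP 6.3 does not change this.

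**Reading 2: baseline as response row and covariate.** Set the baseline SD to 1.

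- The slope shared by the two rows is s = (1 + ρk)/2.
- Baseline-row residual variance: V0 = (1 − s)².
- 6-month-row residual variance: V6 = (ρk − s)² + k²(1 − ρ²).
- The covariance of the two residuals is −((1 − ρk)/2)², which is never positive, so the random-intercept variance is estimated at or near zero.
- The model therefore uses the pooled variance (V0 + V6)/2, while the true variance at 6 months is V6. The ratio is F = 2·V6/(V0 + V6), which cannot exceed 2.
- Type I error ≈ 2 × (1 − Φ(1.96/√F)).

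With equal SDs, F = (5 + 3ρ)/(3 + ρ). At ρ = 0.5, F = 6.5/3.5 = 1.857 and 1.96/1.363 = 1.438, which gives 15.0%. The ceiling F = 2 gives 16.6%.

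Simulated null trials (3,000 per setting, 120 men, REML random-intercept fit, test of the arm effect at 6 months):

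| Setting | Formula | Simulated |
|---|---|---|
| ρ = 0, k = 1 | 12.9% | 12.5% |
| ρ = 0.3, k = 1 | 14.3% | 13.7% |
| ρ = 0.5, k = 1 | 15.0% | 15.2% |
| ρ = 0.7, k = 1 | 15.7% | 15.6% |
| ρ = 0.9, k = 1 | 16.3% | 16.9% |
| ρ = 0.5, k = 0.5 | 9.8% | 10.4% |
| ρ = 0.5, k = 0.75 | 13.1% | 13.3% |
| ρ = 0.5, k = 1.33 | 16.2% | 16.4% |
| ρ = 0.5, k = 2 | 16.6% | 16.9% |

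These fits have a separate arm term at each visit. Leaving out the baseline arm term, as the SAP equation does, changes the results by at most 0.3 points. With 107 men at ρ = 0.5 and k = 1 the figure is 13.5%. Overdispersed counts gave 13.7% to 16.2%. At a joint extreme, ρ = 0.9 with k = 0.5, the formula gives F = 1.239 and 7.8%, so the inflation is smaller there.

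For STI (2,000 runs; assumed prevalence 20% or 30%, odds ratio 1 or 3 between baseline and follow-up, random intercept taken as zero), the same double use of baseline gave 12.6% to 12.9%.

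**Single-visit regression.** The 6-month value on arm, baseline value and covariates, one row per man: 4.2% to 5.6% for CAS across the same settings. Logistic regression for STI on arm and baseline value: 4.5% to 5.6%.

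**The case against.** A reader might infer that the plan yields no CAS analysis at all. The documents do not support that without qualification. lmer() fails only if baseline is kept out of the response, and the promised baseline effect points the other way.

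A reader might also infer that an analyst who meets the error will end up with a test near 14%. That does not follow either. Dropping the random intercept is at least as natural a response and holds about 5%. Overriding the lmer() check gave the same coefficients and standard errors as ordinary regression in the one dataset tried. Using baseline as a response but not as a covariate gave 4.4% to 5.6% with equal SDs, although 0.2% to 12.3% when the SDs differed. Only the double use of baseline gives the inflation tabulated above, and any single figure depends on correlations and SDs that the SAP does not state.

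Three further points have force. The double-use fit was singular in all of 300 lme4 runs at correlation 0.5, and the software reports this by default, although it still prints estimates. The inflation belongs to the 6-month arm contrast: if an arm main effect is added and the arm-by-time interaction is tested instead, rejection was 6.3% to 7.1%. In the SAP equation, which has no arm main effect, the 6-month coefficient is the contrast itself. Finally, the SAP calls the equation a general form and exempts CAS and STI from 3-month output.

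What stands is that the SAP does not choose between the readings, names no fallback for outcomes with one follow-up, and nowhere says to drop the random intercept.

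**Conclusion.** The plan is wrong as written on this point, with limited severity. SAP 6.2 conflicts with itself on the role of baseline. For CAS, covariate-only use gives a model that lmer() will not fit. For STI, glmer() returns a fit with a participant intercept that the data cannot inform. Following both instructions gives a 6-month test that rejects about 10% to 17% of the time at nominal 5%, over correlations of 0 to 0.9 with equal SDs and SD ratios of 0.5 to 2 at correlation 0.5. Both ranges are assumptions, and the joint extreme worked above falls to about 8%.

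The consequence is confined to secondary outcomes of a pilot with no formal power calculation. The primary DBS outcome has two follow-ups and no baseline value, so it is not affected. The ambiguity over baseline does extend to other outcomes measured at all three visits, such as anxiety, depression and PrEP stigma. No error rate was worked out for those.

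**What to change.** In SAP 6.2, state that the baseline value is a covariate where one exists and is never a response row, and remove the promised intervention effect at baseline. This settles the conflict for all outcomes.

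For CAS and STI, add that each is analysed at 6 months only, with no random intercept and no 3-month terms: linear regression for CAS and logistic regression for STI, each on arm, site, the baseline value and the covariates already listed. Report one 6-month effect with its 95% confidence interval per outcome, and no average over visits. Robust standard errors for CAS are optional.

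The cost is one or two sentences of SAP text. No new data, visits or participants are needed.
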